***Next appointment date and time:***

- OK, please write down the date and time in your Activity Book at the bottom of page 11.
- I look forward to speaking next week and hearing how things went!

✓ Session 3 completed	_____ / _____ / _____ month            day            year	_____ / _____ start time        end time	_____ peer initials
-----------------------	--	--	-------------------------------

### Week 4, Session 4: “Diabetes Medications”

**Session Goals:**

- Brief review of last week’s session
- Review DVD: Diabetes Medications
- Review homework
- Learn to connect medicines to future goals
- Your A1c number

**Before Calling the Client** -----

- Review last week’s assignment and the barriers and strategies to overcome them.
- Once you’ve reviewed this, place the call.

**Reminder!!**

- Cover and check off all of the session content.
- Any text in GRAY BOXES is instructions for you: don’t read the text aloud to the client.

Call Log		
Dates	Times	Notes
Attempt 1		 no answer / phone busy  left message / voicemail  rescheduled  bad phone number**
Attempt 2		 no answer / phone busy  left message / voicemail  rescheduled  bad phone number**
Attempt 3		 no answer / phone busy  left message / voicemail  rescheduled  bad phone number**
Attempt 4		 no answer / phone busy  left message / voicemail  rescheduled  bad phone number**
Attempt 5		 no answer / phone busy  left message / voicemail  rescheduled  bad phone number**
Attempt 6		 no answer / phone busy  left message / voicemail  rescheduled  bad phone number**
Attempt 7		 no answer / phone busy  left message / voicemail  rescheduled  bad phone number**
Attempt 8		 no answer / phone busy  left message / voicemail  rescheduled  bad phone number**

**All phone numbers provided are disconnected or 8 call attempts made**	
1. Community coordinator notified (note date / time):  <hr style="width: 100%;"/> 
 date time 
	2. Community coordinator calls back with Next Steps:  <hr style="width: 100%;"/>

**Greeting** -----□

Great, do you have your Activity Book handy?  
*If not, let them get the Activity Book before going on.*

*Say hello and make sure the client is still okay with speaking for about a half hour to forty minutes today.*

Please turn to page 12. Today, we'll review what we learned last week, review your homework, and learn about diabetes medications.

We'll review what you learned on the DVD, and we'll get new homework for this week.

OK, let's get started. Can I ask if you've watched the DVD?

*If they did not watch the DVD, tell them to watch it now, and you'll call back in a half hour.*

**Review Last Week's Session** -----□

OK, let's review what we learned last time. Please stay on page 12.

We talked about the importance of physical activity, which is one of the legs of the three-legged stool. Remember – if you ignore any one of the three legs, it all comes tumbling down!

We learned 3 rules to help us be physically active – can you name them? *Let client answer. If needed, remind client that the 3 rules of physical activity are “Be Smart, Exercise Your Heart,” “Walk Down Your Blood Sugar,” and “Sitting is the New Smoking.”*

We also checked on how you were doing with your medicines, and with healthy eating. You are now actively working on all 3 legs of that stool.

Does that sound right? *Let client answer.* Did you have any questions? *Let client answer.*

**Review DVD: Diabetes Medications** -----□

Great! Let's move on and talk about the DVD you watched this week. How did you like it?  
*Let the client answer and listen supportively.*

Let's review some of the things we saw on the DVD. Please stay on page 12. *Let the client get to the page.*

During this week's video and the first video you watched for this program, you heard some people talk about diabetes medications and how they felt when they were first given medications for their diabetes. What did you think about that? *Listen to their response. Bring out that many people feel reluctant to take medications after finding out that they have diabetes. Emphasize how common it is that people in your communities feel this way at first and don't realize how important medicines are for keeping them well. However, it's never too late to get the benefits of medicines.*

Notes:

- One of the important points made on the video is that the medications are really important for keeping down your blood sugar, but they aren't perfect.
- We learned that diabetes progresses even on medications. This is why you may eventually need a second or third medication even if you're doing everything right.
- Also, we learned that diabetes progresses much more quickly off medications, shortening your life and increasing risks for disabling conditions like stroke, dialysis, heart attack, and amputations.
- These complications can be prevented or delayed with medications, diet, and exercise.
- There are many types of diabetes medications available, so you should be able to get on a medication that both controls your sugar and lets you feel well.
- Side effects can be a problem, but you should discuss with your doctor before stopping. In the video, do you remember what happened with the person that had trouble with her medications at first? *If needed, remind client that she had trouble with her sugar going too low and experiencing stomach upset. However, instead of stopping her medications on her own, she worked with her doctor to find the right medicine for her.*

Notes:

- Finally, the video mentioned how generic medications work as well as brand name drugs, but generics can be more affordable.
- Did you have any questions about what you learned? *If the client has questions that weren't covered in the video, write down the questions and ask the research team. Tell the client you'll ask the doctors in the study and let them know the answer next time. Or, coach the client to ask their doctor their questions. Write down questions in the box below.*

Notes:

**Activity 1: How Medications Can Help Me Live Better, Longer-----**

- Now, let's review some of the things we talked about at our first session. Please turn to page 13. *Go to page 3 in the Client Plan Book and look at what the client told you were some of their hopes for the future.*

- You told me that you wanted to... *read one of their long term goals from page 3*. Is that still important to you? *Listen supportively.*

- *If the client didn't share anything during the first session, encourage them to share something now. Future plans could include something they want to do in retirement, watching a grandchild grow up, attending a family reunion, etc.*
- *If needed, ask them about their loved ones, especially grandchildren or great grandchildren. Suggest something they may want to look forward to in the future, for example, see their great grandchild get married. Add what client shares with you to what you already wrote on page 3 in the Client Plan Book.*

- After watching the video, now you know how diabetes medications are supposed to work for you. How do you think taking the medicines will let you... *[restate their long-term goal]*?
- So, taking your diabetes medication will help you live well now *and* live well in the future, so that you can do the things we just talked about.
- Your diabetes medication will help you have less symptoms of high blood sugar. If you stop your medicine, within a few days, you may feel very tired and thirsty, and you may run to the bathroom all the time.
- On top of you feeling better, day to day, your diabetes medication will help you reach your long-term, future plans so that you're well enough to do what you want to do and to enjoy it.
- If you stop your diabetes medication, in the long run, you'll have higher risks for stroke, heart attack, dialysis, and amputation.
- Many people who have these complications can't live alone anymore.
- Independence is so important for us as we get older. It's great to know there are so many things we can do to improve our chances for remaining independent as long as possible.
- Do you know anyone who lost their independence because of diabetes, or because of a diabetes complication like stroke, amputation, or dialysis? *Encourage them to tell you about a family member or acquaintance who lost their independence. If they don't know anyone, share a personal story of someone you know who lost their independence. Relate this person's story to the client's own future plans. Ask them how they would feel if this happened to them. Ask them whether they'd like to avoid this if possible.*
- If you make sure you are on medicines that you can afford and that agree with you, and you take them every day, you'll feel better now and you'll increase your chances of being well for... *restate the long-term goal again*. How does that sound? *Listen supportively.*

1. *If they are skeptical about the value of the medicines, talk about others like them who you have helped. You may also want to discuss the video clips of Black Belt residents talking about their diabetes and medicines.*
2. *Be supportive and don't criticize. Encourage them to see the value of medicine.*
3. *If they don't want to, be supportive and move on. There will be more opportunities to talk about this later in the program.*

**Activity 2: Are My Diabetes Medications Working for Me?** -----□

- OK, let's be sure that your medicines are working for you.
- The way we tell whether they're working is your A1c number. From your report card that you got at the start of the study, I see that your A1c number was... *read out loud the A1c number on page 2 in the Client Plan Book.*
- On page 13, write in your A1c number into the box.
- Can you tell me what that number means? *Encourage them to tell you how to interpret the number and reinforce what it means. Use the chart below. This is also in their Activity Book.*
- OK, so your number is... *read the category of A1c number, which means it's... read "what it means".*
- Let's talk about what this means in terms of what you should do.

A1c number	What it means	What you should do
Less than 7	Great control	Praise, encourage to keep taking medicine, emphasize if they stop it, A1c will go up
7-8	OK, not perfect	Review diet, exercise, and whether they are taking medicines right. Reinforce importance of taking medicine.
8-9	Cause for concern	Review diet, exercise, how they are taking the medicines. Coach them to talk to their doctor if there has not been a change in the medicines since the A1c was taken. Coach them to call the doctor and ask for more medicine if they are taking it correctly.
9 or higher	Bigger cause for concern	Review diet, exercise, how they are taking medicines. If they are taking medicines correctly, coach them to call the doctor and request more medicine.

- If the number is less than 7, you want to do whatever you can to keep it there. Can you tell me what that is? *Discuss that this is healthy eating, exercise, and taking the medicines as the doctor prescribed.*
- When it's over 7, it's time for action. That's a sign that you may need to make more efforts to eat healthier, exercise more, or get better at taking the medicines.
- Sometimes you are doing all of those things well, but the number is still high. Do you know what that means? *Explain that this happens as diabetes progresses, and some people may have uncontrolled diabetes even if they are doing everything right. It may be time to increase a dose or get another medicine added – both requiring a talk with the doctor.*

*If you decided together that they should reach out to the doctor, discuss in detail how the client will do that.*

- *Many people won't want to call the doctor themselves and may need help. Discuss who in their family can make the call if they don't feel comfortable.*
- *Write down the date of the call and what they'll say when the client calls the doctor in the box below.*

***If you make a plan to reach out to the doctor, call back the day after the planned call by the client/family member to check how things went. If needed, plan together what to do next if things did not go well (for example, if the client never called, or if they never got to talk to the doctor). They may need to make an appointment, and may need help figuring out how to get there. Help them with this.***

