**Activity 1b: Making a Plan for Side Effects and/or Cost Issues -----□**

- OK, you are having trouble taking your medicine because of... *[repeat the side effect and/or cost issue from page 4 of the Client Plan Book]*.
- Your medicine can't help you if you can't take it. Let's make a plan today to reach out to your doctor this week to see what can be done. The doctor can switch you to a different medicine, cut back the dose, or both. *Go to page 5 of the Client Plan Book. Write today's month, day, and year under "Date of plan."*
- First, let's decide who is going to call the doctor. Will you be comfortable calling by yourself? If you'd like to have somebody else on the phone with you, who will it be? *Write down who will be calling the doctor.*
- OK, now, when will you make this call? *Write down the day and time for the call.*
- Finally, let's rehearse what you'll say to the doctor. *Write down what the client will say to the doctor. Have the client repeat what they will say if they hesitate the first time.*
- OK, that sounds like we are beginning to get a plan. Let's think about how hard this may be for you to do. What are some things that might make it hard for you to carry out this plan? *Write down potential barriers.*
- What do you think you can do to overcome these things? *Help clients think of possible ways to overcome these barriers, and write down those solutions.*
- This is great. I look forward to hearing how it went when we talk next week.

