**2) IF ON MEDICINES BUT NOT TAKING CORRECTLY:**

*If they are missing doses because of side effects or cost, be supportive and tell them this happens to a lot of people.*

*Go to page 20 in the Client Plan Book and help client come up with plan on how to reach out to the doctor: who is calling the doctor, when they are calling, what they will say, potential barrier to the plan, and how to get around the barrier. Write down the plan in the Client Plan Book and check back at the next session.*

*If they are not having issues with side effects or cost but still not taking it correctly, supportively correct any mistakes. Tell them a lot of people find this confusing.*

*Go to page 21 in the Client Plan Book and help client make a plan for how to take correctly. Ask client to get their blood pressure rechecked after about a week, possibly at the pharmacist or at the doctor's office with the nurse. Write down the plan in the Client Plan Book and check back at the next session.*

- OK, let's see how that goes. I look forward to hearing about whether the blood pressure is better now that you are taking it like the doctor prescribed.

*Note: here are some common mistakes:*

- ✓ *Twice daily means morning and evening (not 2 doses in the morning)*
- ✓ *Many people skip doses of water pills if they are going out. If they do this, make sure they take it when they come back – don't skip a whole day.*
- ✓ *Some people only take them every other day.*

*When finished, go to **ACTIVITY 3 on page 54 of your manual.***

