## 2) **IF ON MEDICINE BUT NOT TAKING CORRECTLY:**

*If they are missing doses because of side effects or cost, be supportive and tell them this happens to a lot of people.*

*Go to page 24 in the Client Plan Book and help client come up with plan on how to reach out to the doctor: who is calling the doctor, when they are calling, what they will say, potential barrier to the plan, and how to get around the barrier. Write down the plan in the Client Plan Book and check back at the next session.*

*If they are not having issues with side effects or cost but still not taking it correctly, supportively correct any mistakes. Tell them a lot of people find this confusing.*

*Go to page 25 in the Client Plan Book and help client make a plan for taking it correctly. Ask client to get cholesterol rechecked at the doctor's office after about a month. They can wait until their next regularly scheduled visit, which may not be for several months. Write down the plan and check back at the next session.*

- OK, let's see how that goes. I look forward to hearing about how it went and whether you got any side effects now that you will be taking the medicine every day like the doctor prescribed. If you do, we'll make a plan for how to handle that. How does that sound? *Let the client answer.*

*When finished, go to Review of Last Week's Homework on page 57 of your manual.*

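### Minor (participant safety): the Session 4 script can coach a client whose medicine-taking has improved to request more medicine on a pre-coaching A1c, with no prompt to tell the doctor that the reading predates the improvement

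*Combined protocol and SAP*

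**What the plan says.** In Appendix C (Peer Advisor Manual), Session 4, Activity 2, the peer advisor introduces the value with "From your report card that you got at the start of the study, I see that your A1c number was". That reading comes from the baseline visit described under In-Person Biometric Data Collection Visit, before programme materials are handed over and coaching starts.

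A table then links the A1c band to advice. In both bands at 8 or above, the peer first reviews diet, exercise and medicine-taking. For 9 or higher the row continues: "If they are taking medicines correctly, coach them to call the doctor and request more medicine". The 8-9 row gives equivalent advice on the same condition, after a separate sentence: "Coach them to talk to their doctor if there has not been a change in the medicines since the A1c was taken".

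Below the table, the script treats a value over 7 as a possible sign that eating, exercise or medicine-taking needs work. It then adds "Sometimes you are doing all of those things well, but the number is still high", which the peer is to explain as disease progression that may call for a higher dose or another drug.

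If a call is agreed, the peer is told "Write down the date of the call", along with what the client intends to say, in an open box.

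Session 1, Activity 1a has the peer tick, for each diabetes medicine, whether it is being taken as prescribed, and correct any error. Sessions 2 and 3 each review a week of daily medicine logs. The Safety Assessments section names over-control of diabetes through better adherence as a possible harm.

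**The concern.** The advice pairs two facts from different dates: an A1c measured before coaching and a judgement of medicine-taking made after several weeks of it. For a client who took medicines correctly throughout, a high baseline A1c suggests that the regimen is insufficient, and asking for more is reasonable. For a client who began taking them correctly only after the reading, that A1c reflects the earlier, poorer medicine-taking and says little about whether the present regimen is enough.

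The script does not separate these clients, and it does not pass the distinction on to the doctor, who is the person able to use it. Peer advisors are lay people working from a script, and the caller may be a relative, so what is written in the call plan matters. The stake is that a doctor raises treatment without knowing that medicine-taking improved after the value being quoted. That would add modestly to the over-control hazard the protocol already recognises.

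**Working it through.** No sample size, power or analysis figure is involved. The check is a comparison of the texts plus date arithmetic.

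**Age of the reading at Session 4 (target schedule)**

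Inputs from the manual: Session 1 is aimed for within 7 days of the peer receiving the client's name (Client Information), and successive sessions are 7 to 10 days apart (scheduling notes in Sessions 1, 2 and 3).

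- Session 1 to Session 4 is 3 intervals: 3 × 7 = 21 days to 3 × 10 = 30 days.
- Adding 0 to 7 days before Session 1: 21 + 0 = 21 days to 30 + 7 = 37 days.

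This is a target range, not an upper limit. The Session 1 timing is an aim, each session's log allows up to eight call attempts, and the lag from the baseline visit to the peer receiving the name is not stated. The A1c is therefore at least 21 days old if the minimum spacing is kept, and it predates Sessions 1 to 3.

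**Who is coached to request more medicine (A1c 8 or higher)**

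| Correct when A1c taken? | Correct at Session 4? | Coached to request more? | Does the A1c reflect current medicine-taking? |
|---|---|---|---|
| Yes | Yes | Yes | Yes |
| No | Yes | Yes | No |
| Either | No | No | n/a |

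Only the second row is at issue. The script does not distinguish it from the first, because the condition is in the present tense.

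**Does anything shown carry the timing to the doctor?**

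- The 8-9 row's sentence about change since the A1c concerns the medicines, not how they are taken, and governs whether to talk to the doctor, not what to say.
- The call plan asks for the date of the call and the client's words. It prompts neither the date of the A1c nor any change since.
- The scripted explanation for a high value despite good behaviour is progression. For an improved client that is not established, because no newer A1c has been taken in the study.

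**Does the peer already hold the information?**

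Yes. When Activity 2 is reached, the peer has the Session 1 ticks and 7 + 7 = 14 reviewed log days (Sessions 2 and 3) out of 21. The remaining 7 are reviewed later in the same call.

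**The case against.** The strongest reply is that this is a coaching script, not a prescribing rule. The doctor decides. Peer and client must agree before a call is planned. The client has just been told that the A1c dates from the start of the study. The box for what the client will say is open, the peer phones back the day after the planned call, and the programme excludes medical advice and medication management. Low-blood-sugar symptoms are to be assessed during the 12-week phase and reported to the investigators and the physician. Both rows begin by reviewing medicine-taking, so progression is not the first explanation offered. All of this stands and keeps the point minor. None of it prompts anyone to give the doctor the missing fact.

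The materials not shown are a further limit. The Client Plan Book, Activity Book and Health Report Card may print the A1c date or related advice, so the gap is established only for the manual pages shown.

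Four stronger readings are tempting, and the documents do not support them:

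- A reader might infer that every client is affected because non-adherence is an entry criterion. Screening needs only one positive answer on the four-item Morisky scale, and the Session 1 tick allows a medicine to be recorded as taken correctly from the outset.
- A reader might infer that Session 5 handles the same problem properly, because it says "Ask client to get their blood pressure rechecked after about a week" and "Ask client to get cholesterol rechecked". Those instructions are for clients found at that session not to be taking the medicine correctly. For clients who are, Session 5 does what Session 4 does: it uses the report-card value, suggests that the medicine may be insufficient, and points to the doctor.
- A reader might infer a separate defect in the top row, which lacks the 8-9 row's question about a change in the medicines, given that Session 1 tells clients "The doctor can switch you to a different medicine, cut back the dose, or both". A doctor who made such a change would ordinarily know of it.
- A reader might infer harm to the trial's inference. The wording is part of one arm's coaching and does not touch allocation, outcome measurement or analysis.

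**Conclusion.** The concern holds in a narrow form. In the Session 4 script shown, a client with a baseline A1c of 8 or higher who takes medicines correctly now, but did not when the A1c was measured, is coached to ask for more medicine with no prompt to say that the reading predates the improvement. It is a minor participant-safety point, held with medium confidence.

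No headcount can be given: the documents report neither the baseline A1c distribution nor the share of clients whose medicine-taking improves by Session 4. No document figure shows that an increase decided by a physician would be unsafe for these clients, so the added hazard is a reasoned possibility and not a measured one.

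The conclusion assumes that peers follow the script as written, that some clients do improve in Sessions 1 to 3, and that the unseen books do not already supply the date and the change since.

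**What to change.** When a doctor call is planned in the 8-9 row or the 9-or-higher row, add two items to the written call plan: the date of the A1c, and whether medicine-taking or the regimen has changed since. The peer takes the answer on medicine-taking from the Session 1 ticks and the logs reviewed in Sessions 2 and 3. Do not script a request for a repeat A1c. Any recheck or increase is left to the doctor. First check whether the Client Plan Book, Activity Book or Health Report Card already does this.

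Optionally, make the row limits exclusive. At present 8.0 falls in both the 7-8 and 8-9 rows, and 9.0 in both the 8-9 and top rows. With readings to one decimal, the limits could be 7.0-7.9, 8.0-8.9, and 9.0 or higher. This reassigns both 8.0 and 9.0 and should be stated as such. A 9.0 client who is not taking medicines correctly should keep the 8-9 row's advice to talk to the doctor, which would otherwise be lost.

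The cost is a few lines in one session script and a slightly longer call, plus matching edits to the Activity Book chart if the limits change. Some intensification may come later if the doctor chooses to recheck first. Because intervention wording changes, record the date of the manual revision.
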